6.1. General Approach

All patients (treatment and control) will receive standardized sleep education addressing sleep hygiene recommendations that provide guidance on regular bed and wake times; avoidance of alcohol, caffeine, and excessive fluid and food consumption before bedtime; sleeping in dark, cool, and quiet quarters; use of the bed for sleep and intimacy only; avoidance of excessive napping; and avoidance of TV or light exposure before bedtime.

At the end of the baseline visit, after randomization, arrangements will be made to provide each participant a Philips-Respirronics Everflo stationary unit concentrator (active or sham) for in-home use, with optional humidification. This may be through a DME or other local resources. Each unit will contain Bluetooth central monitoring capacity, providing ongoing real-time use

monitoring (indications of flow rates and flow rate changes). The sham model delivers pressurized room air, providing the same sounds and appearances as the active device. Inventories for each device (serial numbers, sham versus active) will be monitored at SRC, and the SRC will instruct the local staff/DME provider as to which specific concentrator (serial number to use).

6.1.1. Nocturnal Oxygen Therapy (Treatment Group)

In the treatment group, supplemental oxygen will be delivered via nasal cannula at a flow rate of 3L/min. If the patient cannot tolerate this flow rate despite efforts to add humidification, the flow may be reduced.

6.1.2. Sham Oxygen (Control Group)

In the control arm, sham oxygen (pressurized room air) will be delivered via nasal cannula at a flow rate of 3L/min. If the patient cannot tolerate this flow rate despite efforts to add humidification, the flow may be reduced.

6.2. Adherence Monitoring and Support

Each oxygen concentrator (sham and active) will be equipped with sensors for monitoring the duration of “on” use and for recording each time an oxygen flow delivery change is made. These data, collected using Bluetooth and cloud-based computer technology, will be monitored by the SRC at weekly intervals for each participant throughout the duration of the study. Sleep Reading Center personnel will be responsible for identifying participants with average oxygen or sham use of < 4 hours/night and relaying this information to the relevant site for follow-up. Clinical site research staff will query participants on hours of use of oxygen (and hours per night of sleep), during each scheduled study call and visit. Clinical site research staff will respond to reports of low adherence by contacting participants by phone to identify possible barriers, concerns, or side-effects that may influence treatment adherence. Following a protocolized telephone-based adherence intervention modeled after ones that have been developed for CPAP (44), they will engage in problem solving, implementing recommend changes such as the addition of humidification (for dryness or nasal discomfort) or changes to address noise. The SRC will centrally train site personnel on techniques of motivational enhancement therapy (MET), a client-centered counseling style designed to increase intrinsic motivation and resolve ambivalence about health behavior change (45,46). Sleep Reading Center personnel recently demonstrated a 1.7 hours/night increase in average adherence to CPAP resulting from a simple MET program (44). With the participant’s permission, a behavioral sleep therapist may join selected calls with the participant and site staff to reinforce MET techniques. The participant and coordinator will be asked not to use any identifying language in order to avoid sharing any PHI the behavioral sleep therapist. Site staff will contact the SRC should problems related to side effects or resistance to treatment be identified that cannot be resolved using the study protocol, and to discuss any interruptions in therapy (due to intercurrent illnesses or other issues). Staff will identify if alternative approaches are needed, consulting with study investigators as needed. All interactions related to adherence (and potential adverse events) will be recorded on Clinical Report Forms.

6.3. Required Training

Site staff and/or the DME provider will instruct patients on usage of the device. The SRC is responsible for site staff training and certification.

6.4. Concomitant Therapy

All participants will be recruited from centers with expertise in managing HF and will be managed with optimal GDMT for HF, according to applicable guidelines in the U.S. (47,48) and Canada (49), including subsequent guideline updates, where stable is defined as the addition of no new class of disease-modifying drug for ≥ 30 days prior to randomization. Reasons for intolerance to GDMT will be documented, as will post-randomization changes in GDMT.

7. Assessing and Reporting of Adverse Events

7.1. Adverse Events

Generally, an Adverse Event (AE) is any untoward clinical occurrence in a study patient. An AE can therefore be any unfavorable and unintended sign (including an abnormal laboratory finding), symptom, or disease. Some AEs may meet the definition of Serious Adverse Event (SAE). Adverse events are either expected or unexpected. Adverse events may also be Unanticipated Problems.

7.1.1. Serious Adverse Events

A Serious Adverse Event (SAE) is any untoward occurrence or effect that:

- Results in death
- Is life threatening
- Requires inpatient unplanned hospitalization or prolongation of existing hospitalization
- Results in persistent or significant disability/incapacity

More than one of the criteria above can be applicable to one event.

Death

Death is defined as either irreversible cessation of circulatory and respiratory functions, or irreversible cessation of all functions of the entire brain, including the brain stem. A determination of death must be made in accordance with accepted medical standards. Thereby the condition leading to death is absolutely circumstantial, whether it occurs as outcome of disease or unnatural causes such as accidents. Efforts will be made to avoid double documentation of death as an outcome of other SAEs and as a dedicated SAE itself.

Life-threatening

The definition of a SAE refers to an event in which the patient was at risk of death at the time of the event; it does not refer to an event that hypothetically might have caused death, if it was more severe.

Hospitalization

Is defined as inpatient care of more than one calendar day (overnight admission). Admission for ambulatory diagnostic procedures, overnight observation visits, or ambulatory visits to an emergency ward are not considered hospitalizations for the purpose of SAE reporting, unless any of the other criteria for serious is met.

7.1.2. Expected Adverse Events

An Expected AE is an AE for which the nature, severity, or degree of incidence is known and identified in the product labeling, published literature, or study protocol or follows the natural

progression of or results from routine treatment of any underlying disease, disorder, or condition of the participant experience the AE. Expected AEs associated with polysomnography, the delivery of NOXT using nasal cannula and an oxygen concentrator, and study participation include: skin irritation (e.g., nose or nares, upper lip, face, area above/behind ears); nasal irritation, inflammation, or dryness; nosebleeds; rhinitis; sinusitis; potential increased incidence of other upper respiratory infection; headache; noise irritation; disrupted sleep; anxiety; falls (tripping over tubing or concentrator); fire hazard; oxygen toxicity. The risk of nosebleeds may be increased in a subset of the study population prescribed an oral anticoagulant or those on antiplatelet (especially dual antiplatelet) therapy. This risk will be mitigated through the provision of humidification to any patient complaining of nasal dryness or discomfort. Excluding patients and/or patients with a bed partner who smokes in bed will mitigate the risk of fire. Patients will also be instructed to avoid the use of (flammable) petroleum-based lotions or creams, like Vaseline, on their face, neck, or upper chest. Patients will be warned about the fall-risk associated with oxygen tubing and the concentrator and instructed on how to avoid tripping, especially when awakening at night to use the bathroom or first thing in the morning, through awareness and through optimal positioning of the concentrator and tubing. Investigators must report any suspected Exemplar Expected AEs above thresholds outlined in the Manual of Procedures (MOP) to the DCC, as soon as possible and within the timeframe specified in the MOP following discovery of the event.

7.1.3. Unanticipated Problems

An unanticipated problem includes any incident, experience, or outcome that meets all of the following criteria:

- unexpected (in terms of nature, severity, or frequency) given (a) the research procedures that are described in the protocol-related documents, such as the IRB-approved research protocol and informed consent document; and (b) the characteristics of the subject population being studied;
- related or possibly related to participation in the research as defined in the MOP; and
- suggests that the research places subjects or others at a greater risk of harm (including physical, psychological, economic, or social harm) than was previously known or recognized.

7.2. Recording and Reporting Adverse Events

At each evaluation, the investigator or research coordinator will determine whether any adverse events (AEs) have occurred. In this trial, all AEs that occur between enrollment and subject exit will be documented in a timely manner and reported to the Data Coordinating Center (DCC). Investigators must report any serious adverse events (SAEs) that are also Unanticipated Problems (events that are unexpected, related or possibly related to the research, and suggest a greater risk of harm to participants or others. to the DCC as soon as possible but no later than 7 days following discovery of the event. The investigator at the site should follow subjects with AEs until the AE has resolved, the condition has stabilized, or the subject exits the trial, and report such follow-up information to the DCC. AEs will be recorded in detail on an AE electronic Case Report Form (eCRF). A description of the event, its severity, and its relatedness to the study intervention will be documented, as well as the resolution of the event. The investigator at the site will adjudicate AEs and assure patient

safety, the DSMB chairperson will receive real-time reports of all USAEs, and the DSMB will periodically review aggregated AE data.

8. Study Schedule

8.1. Study Entry

A patient meets eligibility criteria of the study if the following characteristics are present and documented: all of the inclusion criteria (see Section 6.2.2.) are met and none of the exclusion criteria (see Section 6.2.3.) are met.

8.2. Follow Up and Procedures during the Study Visits/Calls

In-clinic study or remote visits will occur at Screening/Consent, Baseline, 6 months, and 12 months. Telephone follow-up will occur at 1 month, 3 months, 9 months, and 18 months, and then every 6 months after that, until the last participant completes the study. There will be a telephone assessment for each patient at the end of the study, for final ascertainment of mortal and morbid events. Patients potentially meeting eligibility criteria will be consented for further screening. There are two pathways for determination of CSA eligibility for the LOFT-HF trial: a clinical sleep study, polysomnography or home sleep apnea test within 12 months prior to randomization; or a research polysomnogram obtained at home or prior to hospital discharge, when the participant is considered at a baseline, stable condition. The research PSG device is designed for unattended sleep monitoring and contains high quality sensors for quantifying ventilation and oxygenation, and has the ability to measure EEG using self-applied sensors.

Participants will be instructed on how to apply several simple electrodes at home before bed, and return the devices by courier, mail, or direct pick up or drop off. For studies done in the in-patient setting, sensors will be applied by research personnel.

After the results of the clinically-obtained or research PSG are obtained and centrally scored by the SRC, patients meeting sleep eligibility criteria will be invited to participate in a brief baseline examination (remote or in-person) which will include administration of questionnaires (patient-reported outcomes). At the end of the visit, patients will be randomized (stratified by center and the presence or absence of high-risk markers) to sham oxygen (control group) or to NOXT (treatment group). All participants will receive standardized sleep education. A Philips-Respirronics EverFlo stationary concentrator for in-home use will be provided to each participant. Devices will be delivered and installed and patients educated on their use by study staff and/or vendors with established agreements with the study (through a DME company, similar to the INOX trial [<https://clinicaltrials.gov; NCT01044628>]).

Participants will be contacted by telephone (at 1 month, 3 months, 9 months, and 18 months, and then every 6 months after that, until the last participant completes the study) for adverse event and clinical outcomes surveillance. Adverse events and the primary endpoints will be followed until the last subject has undergone a 6-month exam. At 6 and 12 months, subjects will be asked to complete the patient-reported outcomes questionnaires. At study end, each patient and their physician will be provided a copy of relevant clinical information and be offered facilitated referral to a sleep specialist to determine appropriate management of their sleep disorder. Patient-reported outcomes will be collected via validated questionnaires, including the Kansas City Cardiomyopathy Questionnaire (KCCQ), the EuroQol 5D (EQ-5D), the Patient Health Questionnaire-8 (PHQ-8), and the Patient-Reported Outcomes Measurement Information System (PROMIS) Sleep Disturbance and Sleep-Related Impairment Questionnaires. Site personnel will administer these questionnaires, using standard scripted

instructions to patients.

In general, reasonable effort will be undertaken and documented to obtain complete follow up. All follow up visits and calls should be performed within visit windows detailed in Section 8.3, calculated from the date of randomization.

During each study visit and call, the medication taken by the patient as well as the dosage will be recorded. Also, patients will be asked if they take their medication regularly.

Authorized study personnel will document all data requested carefully in the eCRFs, as soon as possible.

8.3. Follow-up Sleep Study and De-briefing Visit

Before the De-briefing Visit, participants will undergo a repeat in-home sleep assessment to serve two purposes: a) provide critical clinical data for use in transitioning to routine clinic care; and b) to maximize the scientific impact of the LOFT-HF study. Participants will be contacted by phone, mail, and/or in-person (coordinating with regularly scheduled clinic or research visits) and offered the opportunity to undergo a repeat in-home research sleep study. The equipment and procedures are the same as described for the research sleep screening visit other than participants will be asked to use their assigned LOFT-HF study treatment during the study and not use the nasal pressure cannula. (The two cannot easily be used together). Devices and equipment will be distributed and returned in-person, by courier, or mail. Study data will be analysed by the BWH SRC, and reports generated with summary data from the overnight sleep study.

At the time of the De-briefing Visit, held on or after Dec 15 2021, when study follow-up will stop, the coordinator will complete assessments for study intervention (sham/NOXT) adherence; collect any pending research data not previously collected (e.g., missing questionnaires); assess for new AEs that occurred up until the final study follow-up date; determine if any medication changes have occurred since last contact thought Dec 15 2021; determine if any clinical outcomes events have occurred through Dec 15 2021; and complete a general rating of improvement/satisfaction survey. After these data are collected, Participants will be provided with a letter that informs the participant of which arm they were randomized to and the results of the baseline and follow-up sleep studies. Participants will be encouraged to discuss further clinical management with their physicians; if needed, the participant will be provided a list of local sleep specialists to access for further clinical follow-up. The coordinator will arrange for return of the oxygen concentrator for final equipment disposition, and if requested, provide a letter to the PCP for continuity of care.

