Statistical Considerations/Sample Size	
We hypothesize a treatment effect resulting in a 20% annual reduction in the primary endpoint (all-cause death, life-saving CV interventions, or hospitalization for worsening HF). This treatment effect is comparable to established therapies for the treatment of HF, such as renin-angiotensin system inhibitors, beta-blockers, and mineralocorticoid receptor antagonists. A total sample of 858 subjects (429 in each arm) achieves 90% power at a 5% significance level to detect a hazard ratio (HR) of 0.755, when the annual event rate in the control group is 40%, using a two-sided logrank test.

---	---

2. Introduction

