4.3. Study duration

Following the start-up phase, the total study duration is expected to be 4.5 years. Patients will be followed up on average for a period of about 2.49 years. All patients will be followed, until the last patient randomized completes 6 months of follow up. Thus, minimum follow up time will be 6 months, and maximum follow up is anticipated to be about 4.5 years. With a randomization rate of 0.35 patients per center per month, 838 patients will be randomized over approximately 54 months of enrollment (although this period may be extended based on COVID-19 pandemic-related enrollment delays). Enrollment contingencies are planned, should the actual randomization rate be higher or lower than that assumed (see Section 10.4.3).

5. Selection and withdrawal of patients

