10.4.2. Years 2-5: Completion of Enrolment or the UH3 Phase

Assuming the accrual pattern is constant across time (after a slower ramp up in the first year for site activation) at 0.35 patients per center per month, the following milestones will be reached within 54 months: 25% of target enrollment (n=215) in Jan 2021, 50% of target enrollment (n=429) in Jan 2022 75% of target enrollment (n=644) in Jan 2023, and 100% enrollment (n=858) in January 2024.

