11.2.5. Interim Analyses

The study will be monitored routinely for issues of data quality, study conduct (including recruitment and follow-up rates), and adverse events. Monthly reports addressing these issues will be provided to the Executive Committee (aggregate [blinded] data). Reports will be provided to the DSMB and NIH every six months or more frequent as requested. We will monitor our primary outcome in planned interim analyses of safety, efficacy and futility.

We plan to perform two interim looks when roughly 30% and 60% of events have occurred. With the proposed design, a total of 520 events are expected and the first interim review for efficacy and futility would be scheduled to occur after approximately 156 primary endpoint events have been observed. It is estimated that this will occur approximately 24 months after enrollment starts, at which time, about 57% of subjects have been enrolled into the study with average follow-up time about 12 months. The second interim review would be scheduled after approximately 312 primary endpoint events have been observed. It is anticipated that the second interim look will occur around 36 months since the initiation of enrollment.

For futility monitoring, we will apply the inefficacy monitoring rule of Freidlin, Korn and Gray (Clinical Trials 2010; 7: 197-208) with a conservative boundary LIB0. For both interim reviews, the LIB0 conservative boundary would suggest stopping the trial for inefficacy if the oxygen arm had a hazard ratio >1.0 compared to the control arm. The Freidlin, Korn, and Gray approach will result in a trivial loss of power and requires no sample size adjustment.

For interim efficacy analyses, we will use the method of Haybittle and Peto. To create a formal framework for assessment of interim results, we will use the Haybittle-Peto boundary. That is, interim results for comparisons of the mortality and HF-related hospitalization rates between treatment groups will be considered sufficient to consider early termination only if the between-group differences are statistically significant at significance level of 0.001. The Haybittle-Peto stopping rule allows the final analysis to be evaluated at a 5% level of significance. As we do not anticipate that the interim analysis will yield efficacy data sufficiently compelling to require early termination, the Haybittle-Peto boundary is particularly suited for this situation.

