We hypothesize a 20% reduction in the 1-year composite event rate, which is high enough to change practice. This effect is within the range of that observed across intervention studies (ranging from 35% for cardiac resynchronization therapy and beta blockers to 15% to 25% for other medications). We anticipate a 1-year event rate of 40% in the control group based on the HF literature showing that patients with advanced HF will experience annual morbidity and

mortality event rates of approximately 40% or greater, especially in the setting of co- morbid CSA.

A total sample of 858 subjects (429 in each arm) achieves 87.9% power at a 5% significance level to detect a hazard ratio (HR) of 0.755 when the 1-year event rate in the control group is 40%, using a two-sided logrank test. We assume a 5% cross-over throughout the study and 10% loss to follow-up throughout the study, and a Cox model with exponential distribution (assuming constant hazard rate), and a 2.49 average length of follow-up.

Original and Revised LOFT-HF Patient Accrual

	Original*	Revised ^{\$}		
Accrual end date	Jan 31, 2023		Jan 31, 2024	
Additional Follow-up Period	12 months	6 months	9 months	12 months
Average length of follow-up	2.75 years	2.49 years	2.74 years	2.98 years
Power	90.2%	87.9%	89.8%	90.4%

*: Corresponds to calculations provided in the original study protocol. Assumes the accrual pattern is uniform over 3.5 years.

\$: Based on the revised projected accrual pattern allowing a slower accrual during siteactivation.

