11.3. Sample Size Calculation

[figure not shown]
We hypothesize a 20% reduction in the 1-year composite event rate, which is high enough to change practice. This effect is within the range of that observed across intervention studies (ranging from 35% for cardiac resynchronization therapy and beta blockers to 15% to 25% for other medications [47,48]). We anticipate a 1-year event rate of 40% in the control group based on the HF literature showing that patients with advanced HF will experience annual morbidity and mortality event rates of approximately 40% or greater (71,72), especially in the setting of co-morbid CSA (18,19). As described in the CCC application and Protocol Draft, several design strategies will be employed to enrich the risk of the enrolled patients. We will not use a run-in design that would select samples with better prognosis.

A total sample of 858 subjects (429 in each arm) achieves 88% power at a 5% significance level to detect a hazard ratio (HR) of 0.755 when the 1-year event rate in the control group is 40%, using a two-sided logrank test. We assume that an accrual period of 4.5 years with a slow ramp up until the end of May 2020, then uniform across the remaining recruitment period until the end of January 2024, and that the study will last until the last enrolled subject completes six-month follow-up. We further assume that the drop-out rate and cross-over rate during the study period are 10% and 5% respectively for both treatment groups.

Conservatively assuming that 35% will screen positive will require screening a total of 2,450 subjects.

We performed sensitivity analyses for power analysis based on varying assumptions of effect sizes (HR=0.72, 0.755, and 0.78) and 1-year event rates in the control group (30%, 35%, and

40%), assuming the same rates of losses to follow-up and cross-over. As shown in the Figure, the proposed sample size achieves over 80% power for most of these settings.

Power for varying effect sizes and 1-year control event rate (1-Survival).

AT=Accrual Time (in Months); T=Total Time (in months).

Our sample size also provides adequate power for key secondary endpoints. Using two-sided tests at 5% significance level, a sample size of 858 provides 80% power to detect 0.2 SD difference in means for a continuous endpoint using a two-sample t-test; to detect a 35%, 23%, and 16% reduction in risks when the risk in the control group is 20%, 40% and 60% for a binary outcome using a Z-test with pooled variance.

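### Section 8.3 stops follow-up on 15 December 2021, about 25 months before planned accrual ends, so the stated 858 patients, 520 events, 88–90% power and 312-event look cannot be delivered on the plan's own milestones

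*Combined protocol and SAP*

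**What the plan says.** Section 8.3 dates the de-briefing visit "held on or after Dec 15 2021, when study follow-up will stop". At that visit the coordinator is to "determine if any clinical outcomes events have occurred through Dec 15 2021", after which participants learn their treatment arm and the concentrator is returned. The words "on or after" qualify only the visit. The stop of follow-up and the cut-off for events are fixed dates.

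Other operative sections of the same document, whose version date is 15 May 2021, describe a longer trial:

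- **Accrual.** Section 10.4.2 gives milestones of 215 patients in January 2021, 429 in January 2022, 644 in January 2023 and "100% enrollment (n=858) in January 2024". Section 11.3 assumes a slow ramp-up to May 2020, "then uniform across the remaining recruitment period until the end of January 2024".
- **Follow-up.** Section 4.3 states: "Patients will be followed up on average for a period of about 2.49 years", with a maximum of about 4.5 years. The Synopsis and Sections 4.3 and 8.2 end follow-up when the last patient reaches 6 months. Section 11.1 continues telephone calls to the last participant's 12-month visit.
- **Events and looks.** Section 11.2.5 expects 520 events, with a first look at about 156. It adds: "The second interim review would be scheduled after approximately 312 primary endpoint events have been observed".
- **Power.** The end of Section 11.2.5 says: "A total sample of 858 subjects (429 in each arm) achieves 87.9% power at a 5% significance level". Section 11.3 gives 88%. The Synopsis and Section 5.2.1 say: "A total sample of 858 subjects (429 in each arm) achieves 90% power at a 5% significance level".

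Section 8.4 sets the de-briefing visit within 6 weeks of the last randomised participant's 6-month visit.

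**The concern.** Two incompatible ends of study stand in one document. Sections 8.3 and 8.4 agree with each other only if the last patient was randomised by about mid-June 2021. In that case accrual to January 2024, and every figure derived from it, no longer describes the trial. If the 2021 date is a mistake, Section 8.3 has coordinators disclose treatment arms and retrieve devices while a double-blind trial still plans some two years of enrolment.

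The stake is how the result would be read. A neutral result from a trial with well under 50% power would sit beside a protocol that states 88–90%. The monitoring plan is triggered by event counts and makes no provision for a calendar stop, so it is also unclear which looks take place.

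**Working it through.** **Inputs from the plan.** Control 1-year event rate 40%; HR 0.755; two-sided 5%; 1:1 allocation; 10% loss and 5% cross-over over the study (Sections 5.2.1, 11.2.5, 11.3). Accrual milestones from Section 10.4.2. First enrolment anticipated in May 2019 (Section 10.4.1).

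**Assumptions the plan does not settle.** Start in May or August 2019; milestones met at the start or the end of January; early accrual linear, or a slow ramp to the end of May 2020. All eight combinations were run. Loss is a constant hazard giving 10% over 2.49 years: −ln(0.90)/2.49 = 0.042 per year.

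**Formulas.**
- Hazards: control −ln(0.60) = 0.5108 per year; treated 0.755 × 0.5108 = 0.3857.
- Expected first events: for a patient followed for time f with hazard λ and loss hazard μ, λ/(λ+μ) × [1 − exp(−(λ+μ)f)], averaged over the two arms and summed over the accrual pattern.
- Power for d events: Φ(√(d/4) × 0.281 − 1.96), where 0.281 = −ln(0.755).
- HR detectable with 80% power: exp(−2 × 2.80/√d).

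**Step 1: reproduce the full plan** (accrual to the end of January 2024, end of July 2024). With loss, this gives 513–526 events, mean follow-up 2.52–2.66 years and power 89–90%. The plan states 520 events, 2.49 years and 87.9–90%. At exactly 520 events the formula gives Φ(11.40 × 0.281 − 1.96) = Φ(1.24) = 89%. The model therefore represents the sponsor's design adequately.

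**Step 2: patients by the stop.** The gap from 15 December 2021 to 31 January 2024 is 25.5 months. Interpolating between 215 and 429:
- Randomised by 15 December 2021: 215 + 214 × 318/365 = 401 (end-January milestones) or 215 + 214 × 348/365 = 419 (start-January).
- Randomised by 15 June 2021, so able to reach 6 months: 215 + 214 × 135/365 = 294 or 215 + 214 × 165/365 = 312.

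**Step 3: events and power at the stop.**

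| | Randomising up to the stop | Only patients who can reach 6 months | Stated |
|---|---|---|---|
| Patients | 401–419 | 294–312 | 858 |
| Mean follow-up (years) | 1.0–1.15 | 1.25–1.46 | 2.49 |
| Events, no loss | 133–154 | 122–143 | – |
| Events, with loss | 130–149 | 118–138 | 520 |
| Power at HR 0.755 | 36–41% | 33–39% | 87.9–90% |

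At the extremes, 118 events give Φ(5.43 × 0.281 − 1.96) = Φ(−0.43) = 33%, and 154 give Φ(6.20 × 0.281 − 1.96) = Φ(−0.22) = 41%. The HR detectable with 80% power is exp(−5.60/√118) = 0.60 to exp(−5.60/√154) = 0.64. Maximum follow-up from May 2019 is about 2.6 years, against about 4.5 stated.

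These power figures ignore cross-over. If the 5% cross-over fully dilutes the HR to 0.777, power at the stop is about 29–35%, but the full plan then has only about 82%, so that treatment does not reproduce the stated figure.

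**Step 4: what fails without a model.** Each patient contributes at most one first event. With at most about 420 patients, 858 patients and 520 first events are out of reach whatever the event rate.

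**Step 5: interim looks.** If accrual and follow-up continued, 312 events would fall between February and April 2023, some 14 months or more after the stop. The first look is a near miss: 156 events would fall between late December 2021 and March 2022. The blinded re-estimation point (43% of 858, or 369 patients) falls in September–October 2021, before the stop, so nothing here shows that it is missed. The statement in Section 11.2.5 that 57% are enrolled at 24 months matches the superseded uniform 42-month accrual (24/42 = 57%).

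**Step 6: a more favourable accrual.** The superseded uniform 3.5-year accrual would give 581–643 patients, 217–263 events and 54–63% power at the stop. The stated figures are still missed.

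**The case against.** The strongest defence is that the date is a deliberate early close-out. The version is dated seven months before the stop, and Section 8.3 sets out an orderly ending. Section 5.3.1 allows discontinuation when enrolment milestones are not substantively met. A design-stage sample size does not become false because a trial closes early, and keeping it as the record of the planned design is legitimate. A rationale or a revised monitoring plan may also lie in text not supplied for this review, so nothing should be inferred about what the oversight bodies knew.

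Much of this is fair, and it affects how the point is put. The power figures assume that planned milestones were met. Actual enrolment is not in the documents, and Section 4.3 itself warns of COVID-19 delays. The first look is planned at approximately 156 events, so an upper projection of 154 is too close to call it missed. No reconstruction matches 2.49 years exactly, so conclusions that turn on a few events should not be drawn.

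The contradiction remains. Sections 4.3, 10.4.2, 11.2.5 and 11.3 are written as the current plan and not as a superseded design, and an explanation held elsewhere would not change what they say. Choices of loss model move power by about one percentage point.

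**Conclusion.** The point holds, and it needs to be fixed. As written, the document has two ends of follow-up that cannot both apply. Under the Section 8.3 date and the plan's own milestones, the trial would have about 400–420 patients (about 295–310 with 6 months of follow-up), 118–154 events (23–30% of 520) and 33–41% power at HR 0.755. It would miss its target effect roughly six times in ten or more.

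That 858 patients and 520 events cannot be reached depends only on the accrual milestones. That the 312-event look cannot be reached also depends on the 40% control rate. The power figures further depend on constant hazards and on no dilution from cross-over. All are projections from planned accrual. The documents do not show which date the sponsor intends, and this review does not choose one.

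**What to change.** Adopt one end-of-follow-up rule, and make the Synopsis and Sections 4.3, 5.2.1, 8.2, 8.3, 8.4, 10.4.2, 11.1, 11.2.5 and 11.3 agree with it.

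- **If 15 December 2021 is the stop date:** state the N, events, average follow-up, power and detectable HR expected at that date from actual enrolment. The planned design can be kept if it is labelled as superseded, for example in a dated addendum. State that the 312-event look will not take place, unless actual event counts show otherwise. State whether the first look and the blinded sample size re-estimation have taken place or will.
- **If it is not the stop date:** remove it from Section 8.3, and make event collection, disclosure of treatment arm and device return there refer to the same end-of-follow-up rule as Sections 8.2 and 8.4.
- **In either case:** reconcile the 12-month wording in Section 11.1 with the 6-month rule elsewhere.

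The cost is a text amendment and, if the date stands, less favourable stated figures. No patients or procedures are added.
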